# 9.1.3. Other/Exploratory Assessments

**Eight-item Interview to Differentiate Aging and Dementia (AD8; Galvin et al. 2005).** The Washington University Dementia Screening Test, also known as AD8, is completed by the study partner. This test is sensitive to detecting early cognitive changes and has a total score range of 0-8. This test is added to explore performance as a simple screening tool.

Repeatable Battery for the Assessment of Neuropsychological Status (RBANS; Randolph et al. 1998; Duff et al. 2008). The RBANS is a collection of 12 subtests representing 5 neurocognitive domains: Immediate Memory, Visuospatial/Constructional, Language, Attention, and Delayed Memory. The raw scores from each subtest within a domain are converted to a summary score, or Index Score, for the domain by consulting normative data tables. The RBANS also provides an overall Index Score that summarizes the patient's overall level of performance on this measure.

Administration of the RBANS will be audio-recorded for quality-control and training purposes. Audio recordings will be centrally reviewed and monitored where permitted by local law.

**EuroQoL-5D (EQ-5D; Kind 1996).** The EQ-5D (proxy versions) is a standardized instrument used to measure overall health status and is applicable to a wide range of health conditions and treatments. It provides both a descriptive profile and a single index value for health status. The 5D in the name refers to the 5-dimensional classification system for health states used in the instrument. Each dimension (mobility, self-care, usual activities, pain/discomfort, and anxiety/depression) has 3 levels of severity (no, some, and severe problems). Scores on individual dimensions are recorded, as is a total score that sums the individual dimension scores. A visual analog scale (VAS) also assesses the caregiver's impression of the patient's overall health state. Reliability and validity for use with an AD population have been demonstrated (Jönsson et al. 2006; Naglie et al. 2006). Scores can be converted into weighted health state preferences for quality-adjusted life year models.

Quality of Life in Alzheimer's Disease (QoL-AD; Logsdon et al. 2002; Thorgrimsen et al. 2003). The QoL-AD is a disease-specific measure of quality of life for an AD population. It includes 13 items, each rated on a 4-point scale. Summing the items provides an overall score to index the patient's quality of life. The QoL-AD is administered to the patient by a rater and asks the patient to provide ratings on mood, relationships, memory, finances, and so on. The patient's primary caregiver also is asked to complete the same measure. Reliability and validity in samples of AD patients and their caregivers have been demonstrated.

Resource Utilization in Dementia—Lite questionnaire (RUD-Lite; Wimo et al. 1998). The RUD-Lite is designed to assess the healthcare resource utilization of patients and their caregivers and to determine the level of formal and informal care attributable to AD. The data are collected through a structured interview. Information on both caregivers (caregiving time, work status) and patients (accommodation and healthcare resource utilization) is gathered from the baseline and final assessment interviews. Caregivers will be asked to provide data on time spent assisting patients' basic ADLs such as using the toilet, eating, dressing, grooming, walking, and bathing; assisting patients' instrumental ADLs such as shopping, cooking, housekeeping, laundry, transportation, taking medication, and managing finances; and providing supervision. The resource utilization quantified by the RUD-Lite can be used for calculating cost offsets and in cost-effectiveness models.

## 9.1.4. Appropriateness of Assessments

The ADAS-Cog is a widely accepted, validated clinical outcome measure. The scale reflects domains and abilities that are central to the characterization of an AD patient's deficits in a clinical setting and its items are linked to meaningful aspects of the lives of patients and caregivers. Furthermore, the scale has demonstrated its ability to detect treatment differences in the span of MCI and mild AD (Aronson et al. 2009; Orgogozo et al. 2004; Salloway 2004).

# 9.1.5. Order of Efficacy Assessments and Rater Qualifications

Assessments administered to the patient include the MMSE, ADAS-Cog13, RBANS, QoL-AD and CDR. Assessments administered to the study partner include the AD8, CDR, FAQ, ADCS-ADL, NPI, EQ-5D, QoL-AD, and RUD-Lite.

Table 9.1 lists the relative sequencing of tests for both patient and study partner.

It is recommended that efficacy assessments be performed as the first activity at all specified visits. Additionally, it is recommended that, during these visits, cognitive and functional tests are performed in the sequence, if performed at the same visit, as shown in Table 9.1.

The CDR should always be administered to the study partner first and then to the patient; the study partner and patient must be interviewed separately. It is important to maintain the same test sequence at each visit for each patient throughout the study. Assessments should be scheduled to allow the cognitive testing to be performed at approximately the same time of the day (±4 hours) at all the visits to avoid the known circadian variation of cognitive performance (Higuchi et al. 2000). Patients and study partners should be assessed separately, because the presence of the other person may potentially contaminate the results of an assessment. When necessary, patients should be allowed a rest break between cognitive tests. Based on rater judgment, other nonstressful study procedures may be conducted during these breaks.

There should be at least two raters at each site. The sites can determine which rater does what scale. However, the ADAS-Cog13 should have a different rater than the rater who performs the CDR, ADCS-ADL, and FAQ for each patient. All other scales may be performed by any rater.

Table 9.1. Order of Test Administration for Patient and Study Partner

Patient	Study Partner
1. MMSE	Screening Visit 1. AD8

2. ADAS-Cog13 (Rater 1)

3. RBANS

	2. CDR (Rater 2)
4. QoL-AD	Enrolled Visits 1. FAQ (Rater 2)
5. CDR (Rater 2)	
 
ADCS-ADL (Rater 2)
 
CDR (Rater 2)
 

	4. NPI
	5. EQ-5D 6. QoL-AD
	7. RUD-Lite

Abbreviations: AD8 = Eight-item Interview to Differentiate Aging and Dementia; ADAS-Cog13=13-item Alzheimer's Disease Assessment Scale – Cognitive subscale; ADCS-ADL=Alzheimer's Disease Cooperative Study Activities of Daily Living Inventory; CDR = Clinical Dementia Rating; EQ-5D Proxy = 5-dimensional EuroQol quality of life scale; FAQ=Functional Activities Questionnaire; MMSE=Mini-Mental State Examination; NPI=Neuropsychiatric Inventory; QoL-AD = Quality of Life in Alzheimer's Disease; RBANS= Repeatable Battery for the Assessment of Neuropsychological Status; RUD-Lite=Resource Utilization in Dementia – Lite.

#### 9.2. Adverse Events

Investigators are responsible for monitoring the safety of patients who have entered this study and for alerting the Sponsor or its designee to any event that seems unusual, even if this event may be considered an unanticipated benefit to the patients.

The investigator is responsible for the appropriate medical care of patients during the study.

Investigators must document their review of each laboratory safety report.

The investigator remains responsible for following, through an appropriate health care option, AEs that are serious or otherwise medically important, considered related to the investigational product or the study, or that caused the patient to discontinue the investigational product before completing the study. The patient should be followed until the event resolves, stabilizes with appropriate diagnostic evaluation, or is reasonably explained. The frequency of follow-up evaluations of the AE is left to the discretion of the investigator.

Lack of drug effect or expected clinical progression is not an AE in clinical studies, because the purpose of the clinical study is to establish treatment effect.

After the informed consent form (ICF) is signed, study site personnel will record via electronic case report form (eCRF) the occurrence and nature of each patient's preexisting conditions,

including clinically significant signs and symptoms of the disease under treatment in the study. In addition, site personnel will record any change in the condition(s) and any new conditions as AEs. Investigators should record their assessment of the potential relatedness of each AE to protocol procedure and/or investigational product(s), via eCRF.

The investigator will interpret and document whether or not an AE has a reasonable possibility of being related to study treatment, PET tracers, or a study procedure taking into account the disease, concomitant treatment(s), or concurrent pathologies/conditions.

A "reasonable possibility" means that there is a cause and effect relationship between the investigational product, PET tracers and/or study procedure and the AE.

The investigator answers yes/no when making this assessment.

Planned surgeries and nonsurgical interventions should not be reported as AEs unless the underlying medical condition has worsened during the course of the study.

If a patient's investigational product is discontinued as a result of an AE, study site personnel must report this to the Sponsor or its designee via eCRF clarifying, the circumstances leading to any dosage modifications, or discontinuations of treatment.

#### 9.2.1. Serious Adverse Events

An SAE is any AE from this study that results in one of the following outcomes:

- death
- initial or prolonged inpatient hospitalization
- a life-threatening experience (that is, immediate risk of dying)
- persistent or significant disability/incapacity
- congenital anomaly/birth defect
- considered significant by the investigator for any other reason: important medical events that may not result in death, be life-threatening, or require hospitalization may be considered serious, based upon appropriate medical judgment.

Although all AEs occurring after signing the ICF are recorded in the eCRF, SAE reporting begins after the patient has signed the ICF and has received investigational product or PET imaging. However, if an SAE occurs after signing the ICF, but prior to receiving investigational product or PET imaging, it needs to be reported ONLY if it is considered reasonably possibly related to study procedure.

Study site personnel must alert the Sponsor or its designee of any SAE within 24 hours of investigator awareness of the event via a sponsor-approved method. If alerts are issued via telephone, they are to be immediately followed with official notification on study-specific SAE forms. This 24-hour notification requirement refers to the initial SAE information and all follow-up SAE information.

Pregnancy (during maternal or paternal exposure to investigational product) does not meet the definition of an AE. However, to fulfill regulatory requirements any pregnancy should be reported following the SAE process and subject should be consented to collect data on the outcome for both mother and fetus.

Investigators are not obligated to actively seek AEs or SAEs in subjects once they have discontinued and/or completed the study (the patient summary eCRF has been completed). However, if the investigator learns of any SAE, including a death, at any time after a subject has been discharged from the study, and he/she considers the event reasonably possibly related to the study treatment or study participation, the investigator must promptly notify the Sponsor or its designee.

#### 9.2.1.1. Suspected Unexpected Serious Adverse Reactions

Suspected unexpected serious adverse reactions (SUSARs) are serious events that are not listed in the IB and that the investigator identifies as related to investigational product or study procedure. United States 21 CFR 312.32 and European Union Clinical Trial Directive 2001/20/EC and the associated detailed guidances or national regulatory requirements in participating countries require the reporting of SUSARs. The Sponsor has procedures that will be followed for the recording and expedited reporting of SUSARs that are consistent with global regulations and the associated detailed guidances.

# 9.2.2. Complaint Handling

The Sponsor collects product complaints on investigational products and drug delivery systems used in clinical studies in order to ensure the safety of study participants, monitor quality, and to facilitate process and product improvements.

Patients will be instructed to contact the investigator as soon as possible if he or she has a complaint or problem with the investigational product so that the situation can be assessed.

#### 9.3. Treatment of Overdose

Additional details regarding treatment of overdose are provided in the IB.

# 9.4. Safety

# 9.4.1. Electrocardiograms

For each patient, electrocardiograms (ECGs) should be collected according to the Schedule of Activities (Section 2). Electrocardiograms should be recorded according to the study specific recommendations included in the ECG central vendor's Manual of Operations for the study.

Electrocardiograms will initially be interpreted by a qualified physician (the investigator or qualified designee) at the site as soon after the time of ECG collection as possible, and ideally while the patient is still present, to determine whether the subject meets entry criteria at the relevant visit(s) and for immediate patient management, should any clinically relevant findings be identified.

All digital ECGs will be electronically transmitted to a designated central ECG laboratory. A cardiologist at the central ECG laboratory will then conduct a full overread. A report based on data from this overread will be issued to the investigative site. Any clinically significant findings from ECGs that result in a diagnosis and that occur after the patient receives the first dose of the investigational treatment should be reported to the Sponsor or its designee as an AE via eCRF per Section 9.2.

The Principal Investigator or physician delegate is responsible for reviewing all ECGs. Patient must meet eligibility criteria with respect to cardiac inclusion/exclusion criteria at the time of the screening.

Unscheduled ECGs may be obtained at the discretion of the investigator.

## 9.4.2. Vital Signs

For each patient, vital signs measurements, including temperature, should be conducted according to the Schedule of Activities (Section 2) at all office visits. Blood pressure and pulse will be measured supine and standing. Supine blood pressure and pulse rate should be taken after at least 5 minutes of supine rest. Standing blood pressure and pulse rate should be taken after 2 and 5 minutes in a standing position. Temperature will be recorded using an oral or tympanic thermometer.

Any clinically significant findings from vital signs measurement that result in a diagnosis and that occur after the patient receives the first dose of study treatment should be reported to the Sponsor or its designee as an AE via eCRF per Section 9.2.

# 9.4.3. Physical and Neurological Examinations

Complete physical examinations, brief physical exams, and complete neurological exams will be performed according to the Schedule of Activities (Section 2). The complete physical examination will include assessment of the following: general appearance; skin, head and neck; lymph nodes; thyroid; abdomen (bowel sounds, liver and spleen palpation); back (costovertebral angle tenderness); and musculoskeletal, cardiovascular, and respiratory systems. The brief physical examination will include assessments of the skin, lungs, cardiovascular system, and abdomen (bowel sounds, liver and spleen palpation).

Complete neurological examinations will be conducted and will include a thorough assessment of gait, balance, coordination, cranial nerves, sensory and motor systems, and reflexes. A neurologist will be consulted in the event of significant new neurological findings.

Body weight and height will be recorded according to the Schedule of Activities (Section 2).

Any clinically significant changes on follow-up physical and neurological examinations should be reported to the Sponsor or its designee as an AE via eCRF per Section 9.2.

# 9.4.4. Laboratory Tests

For each patient, laboratory tests detailed in (Appendix 2) should be conducted according to the Schedule of Activities (Section 2).

Scheduled laboratory tests are performed by a central vendor. Any clinically significant findings from laboratory tests that result in a diagnosis and that occur should be reported to the Sponsor or its designee as an AE via eCRF per Section 9.2.

#### 9.4.5. C-SSRS

Consistent with Food and Drug Administration (FDA) regulatory guidance (FDA 2012), any occurrence of suicide-related thoughts and behaviors will be assessed as indicated in the Schedule of Activities (Section 2). The Columbia Suicide Severity Rating Scale (C-SSRS) is a scale that captures the occurrence, severity, and frequency of suicide-related thoughts and behaviors during the corresponding assessment period. The scale includes suggested questions to elicit the type of information needed to determine if a suicide-related thought or behavior occurred.

The C-SSRS is available in an adult's and a children's version. There is no version of the C-SSRS designed for use in a cognitively impaired population such as patients with AD; therefore, the children's version will be used. Terms captured by the use of the C-SSRS children's version can be mapped to Columbia Classification Algorithm for Suicide Assessment (Posner et al. 2007), to facilitate future pooling of data.

The first time the scale is administered in this study (at Visit 2), the C-SSRS "Baseline/Screening" version will be used, and the findings will constitute the baseline assessment. The C-SSRS "Since Last Visit" version will be used for all subsequent assessments. The C-SSRS will be administered to the patient with the caregiver/study informant present, after the cognitive and functional assessments. Responses from both the caregiver/study informant and patient will be considered when administering the scale. If a suicide-related thought or behavior is identified at any time during the study, a thorough evaluation will be performed by a study physician, and appropriate medical care will be provided.

The Lilly Self-Harm Supplement should be completed every time the C-SSRS is administered. If, based on administration of the C-SSRS, it is determined that suicide-related behaviors have occurred, then the Lilly Self-Harm Follow-Up form will be used to collect additional information to allow for a more complete assessment of these behaviors.

Any clinically significant findings from the C-SSRS should be reported to the Sponsor or its designee as an AE via eCRF per Section 9.2.

# 9.4.6. Magnetic Resonance Imaging (Safety)

Magnetic resonance imaging of the brain will be performed according to the Schedule of Activities (Section 2) and as clinically indicated. This technology will be used to check for evidence of Amyloid Related Imaging Abnormality (ARIA-Hemmorhage [ARIA-H] and ARIA-Edema [AIRA-E]). ARIA-Edema is associated with immunotherapies; no association is currently known for LY3314814. See Section 9.4.9.4 regarding vasogenic edema for additional information. The MRI data will also be used to calculate brain volumes as a potential efficacy biomarker.

The MRI scans will be sent for analysis to a centralized MRI vendor designated by the Sponsor. The scans will be reviewed by the investigator or qualified designee for immediate patient management. Study eligibility will be determined by central vendor read. Any clinically significant findings from MRI that result in a diagnosis should be reported to the Sponsor or its designee as either a pre-existing condition or AE via eCRF per Section 9.2. Specific analyses of the scans including assessments of ARIA-H and ARIA-E and calculations of brain volumes will subsequently be interpreted by the centralized MRI vendor for data analysis and report-writing purposes. Results of centrally read MRIs regarding patient care/safety will be reported back to sites even though there was a local read.

# 9.4.7. Eye examination

A comprehensive eye examination, to include corrected visual acuity, intraocular pressure, a slit lamp examination, and a dilated fundus examination (dilation only performed in patients without contraindication to mydriatics), will be performed at the times shown in the Schedule of Activities (Section 2). The eye examinations must be reviewed and/or performed by an optometrist or ophthalmologist, preferably using the same optometrist or ophthalmologist for each patient's visit. Patients who complain of vision disturbance during the clinical trial should be referred to the optometrist or ophthalmologist for unscheduled evaluation.

Any clinically significant findings that result in a diagnosis should be recorded to the Sponsor or its designee as a pre-existing condition or AE via eCRF per Section 9.2. The principal investigator will make all final determinations of AEs in consultation with performing eye examiner.

#### 9.4.8. Skin examination

A complete skin examination will be performed at the times shown in the Schedule of Activities (Section 2).

All skin examinations must be reviewed and/or performed by a dermatologist who will inspect the patient's unclothed full body using a UV light. The initial examination will include the Fitzpatrick skin-type classification scale. The follow-up skin examinations will preferably be completed for a given patient by the same dermatologist who conducted the initial examination.

At each examination, abnormal hypopigmentation will be assessed by location, percentage of body surface area involvement, degree (partial/decreased pigmentation to complete depigmentation), and other findings in or around the hypopigmented area (such as redness or induration). A static physician's global assessment will be used to determine the patient's overall hypopigmentation severity at a given timepoint using a visual analog scale (VAS) ranging from 0 to 100. In addition, patients noted to have evidence of hypopigmentation will be asked to record how bothersome they find the hypopigmentation on a VAS ranging from 0 to 100. Skin photographs may be taken as appropriate for generating supporting documentation, but not for the purpose of primary clinical dermatologic evaluation or for data generation or analysis. A punch biopsy may be obtained at the discretion of the dermatologist.

Any clinically significant findings that result in a diagnosis should be recorded to the Sponsor or its designee as a pre-existing condition or AE via eCRF per Section 9.2. The principal investigator will make all final determinations of AEs in consultation with the dermatologist.

## 9.4.9. Safety Monitoring

The Sponsor will periodically review evolving aggregate safety data within the study by appropriate methods.

If a study patient/subject experiences elevated ALT  $\geq$ 3X ULN, ALP  $\geq$ 2X ULN, or elevated TBL  $\geq$ 2X ULN, hepatic clinical and laboratory monitoring should be initiated by the investigator. In the presence of Gilbert syndrome, isolated elevation of bilirubin with normal ALT, AST, and ALP may not require additional evaluation. Details for hepatic monitoring depend upon the severity and persistence of observed laboratory test abnormalities. To ensure patient safety and comply with regulatory guidance, the investigator is to consult with the Sponsor-designated medical monitor regarding collection of specific recommended clinical information and follow-up laboratory tests. Additional hepatic eCRF should be completed for these patients as information becomes available. See Appendix 4.

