### 8. Discontinuation Criteria

# 8.1. Discontinuation from Study Treatment

## 8.1.1. Discontinuation from Study Treatment

Discontinuation of the investigational product for abnormal liver tests **should be considered** by the investigator when a patient meets one of the following conditions after consultation with the Sponsor-designated medical monitor:

- alanine aminotransferase (ALT) or aspartate aminotransferase (AST) >8X upper limit of normal (ULN)
- alanine aminotransferase or AST >5X ULN for more than 2 weeks
- alanine aminotransferase or AST >3X ULN and total bilirubin level (TBL) >2X ULN or prothrombin time >1.5X ULN
- alanine aminotransferase or AST >3X ULN with the appearance of fatigue, nausea, vomiting, right upper-quadrant pain or tenderness, fever, rash, and/or eosinophilia (>5%)
- Alkaline phosphatase (ALP) elevations, if deemed of liver origin and drug-related as follows:
  - ALP >3X ULN
  - ALP >2.5X ULN and TBL >2X ULN
  - ALP >2.5 ULN with the appearance of fatigue, nausea, vomiting, right quadrant pain or tenderness, fever, rash, and/or eosinophilia (>5%)

In addition, patients **must** be discontinued from the investigational product in the following circumstances:

- Patient decision. The patient may discontinue treatment, without prejudice to further treatment, at any time.
- Adverse event or clinically significant laboratory value, ECG result, or vital sign
  measurement of such severity that, in the opinion of the investigator or medical monitor,
  continued treatment is not in the best interest of the patient
- Severe non-compliance to the study protocol that results in a safety concern, in the judgment of the investigator
- The patient, for any reason, requires a treatment with an excluded therapeutic agent and temporary discontinuation criteria can't be met (see Section 8.1.2)
- The patient develops a significant uncontrolled medical condition that in the opinion of the investigator after appropriate medical assessment, would pose an unacceptable risk to the patient if they were to continue receiving investigational product.

Patients who discontinue the investigational product early will have early discontinuation procedures performed as shown in the Schedule of Activities (Section 2).

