**Optional** 

(tested at the discretion of the investigator or if mandated by local regulatory authority)

Human immunodeficiency virusa

Abbreviations: HDL = High-density lipoproteins; LDL = Low-density lipoproteins; PCR = polymerase chain reaction; RBC = red blood cells; WBC = white blood cells.

- a At screening only.
- b Done at all other times besides screening.
- c At screening only in patients with suspected or past history of Hepatitis B.
- d At screening only in patients with suspected or past history of Hepatitis C.
- e At screening, Week 26, Week 52, and Week 78 (or final study visit) only for the Placebo-Controlled period as well as Week 104, Week 130, and Week 156 (or final study visit) only for the Delayed-Start period.

Note: Laboratory values outside the reference limit suspected to be of any clinical significance will be repeated. Patients for whom suspected clinical significance is confirmed will either not be enrolled or, if already enrolled, will be followed until normalization or for as long as the Investigator considers necessary. Additional laboratory tests may be performed for safety reasons if judged appropriate by the investigator. See Section 9.4.4 for information regarding the recording of AEs based on laboratory tests. All laboratory samples will be analyzed using routine methods per the central laboratory, as referenced in the Laboratory Manual for this study.

For blood volume, see Appendix 5.

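### Protocol 9.4.9 sets no AST level for starting hepatic monitoring or the hepatic eCRF, although all four transaminase criteria in 8.1.1 for considering discontinuation accept AST

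*Protocol*

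**What the plan says.** Protocol 9.4.9 (Safety Monitoring) gives three numerical triggers: ALT ≥3X ULN, ALP ≥2X ULN and TBL ≥2X ULN. When one is met, "hepatic clinical and laboratory monitoring should be initiated by the investigator", and the investigator consults the sponsor-designated medical monitor about clinical information and follow-up tests. It adds: "Additional hepatic eCRF should be completed for these patients as information becomes available". AST appears in that paragraph only in the Gilbert syndrome exemption, where it must be normal. The extent of the work-up is left flexible: "Details for hepatic monitoring depend upon the severity and persistence of observed laboratory test abnormalities".

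Protocol 8.1.1 lists four transaminase criteria for considering discontinuation, and each can be met by ALT or by AST. They are a value above 8X ULN; "alanine aminotransferase or AST >5X ULN for more than 2 weeks"; a value above 3X ULN together with TBL above 2X ULN or prothrombin time above 1.5X ULN; and "alanine aminotransferase or AST >3X ULN with the appearance of fatigue" or other listed symptoms or eosinophilia. Three further criteria concern ALP.

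Section 9.4.9.1 makes liver toxicity an adverse event of special interest and cites both 9.4.9 and 8.1.1. AST is on the routine chemistry panel in Appendix 2.

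**The concern.** The two sections should work as a sequence: a lower threshold starts the liver work-up, and a higher or more complicated finding raises the question of stopping drug. For ALT and ALP they do. For AST the first step is missing, so an isolated AST rise can arrive at the discontinuation question without any fixed rule having called for the hepatic work-up or the hepatic eCRF.

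The documents give no reason for leaving AST out. Exclusion criterion 31 applies the same limit to both enzymes (≥2X ULN), as does SAP Appendix 3 (≥3X ULN). SAP 6.13.4 does lean towards ALT, with tiers up to ≥10X ULN against a single AST tier at ≥3X ULN, but that concerns tabulation, not patient management.

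At stake is how early and how uniformly standard hepatic information is gathered for a safety topic that the protocol singles out.

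**Working it through.** No sample size, power or error rate is involved, and the plan states no figure to reproduce. The check sets the 9.4.9 triggers against each 8.1.1 criterion and asks whether meeting the criterion forces a trigger to be present.

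**Inputs.** Triggers from 9.4.9: ALT ≥3X, ALP ≥2X, TBL ≥2X ULN. Criteria from 8.1.1: four transaminase and three ALP. In the third transaminase criterion I read prothrombin time as an alternative to TBL, with either one accompanying the transaminase rise. For the AST route, take a patient with ALT <3X and ALP <2X ULN, and with TBL <2X ULN unless the criterion itself requires more.

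| 8.1.1 transaminase criterion | Met through ALT | Met through AST |
|---|---|---|
| Above 8X | ALT trigger present (8 > 3) | No trigger |
| Above 5X for more than 2 weeks | ALT trigger present (5 > 3) | No trigger |
| Above 3X with TBL above 2X | ALT trigger present | Trigger present, through TBL |
| Above 3X with prothrombin time above 1.5X | ALT trigger present | No trigger |
| Above 3X with symptoms or eosinophilia | ALT trigger present | No trigger |

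Rows three and four are the two limbs of one criterion.

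**ALP route.** The three criteria are ALP above 3X, above 2.5X with TBL above 2X, and above 2.5X with symptoms. Each exceeds 2X, so each carries the ALP trigger.

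**Count of criteria that guarantee a 9.4.9 trigger.**
- ALT: 4 of 4.
- ALP: 3 of 3.
- AST: 0 of 4. Three criteria can be met with no trigger at all. The third criterion carries one through its TBL limb only, and its prothrombin limb does not.

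**Prothrombin time.** Appendix 2 marks it as a screening-only test. After screening it is listed only in the Appendix 4 hepatic panel. For a patient whose only abnormality is AST above 3X, no fixed rule therefore leads to the test on which the prothrombin limb depends. With ALT ≥3X, 9.4.9 at least starts monitoring and refers to Appendix 4.

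**A trigger elsewhere?** Appendix 4 speaks of a treatment-emergent hepatic abnormality without giving a level. The Appendix 2 note gives none. SAP 6.13.4 refers to criteria for completing the hepatic CRF but does not restate them.

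**After the change.** With AST ≥3X ULN as a trigger, every AST criterion (above 8X, 5X, 3X and 3X) carries one, so the count becomes 4 of 4.

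**The case against.** The best case for the current wording is that a trigger list is a minimum and other provisions cover most of the ground.

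- The Appendix 2 note says: "Laboratory values outside the reference limit suspected to be of any clinical significance will be repeated". Confirmed cases are then followed.
- Section 8.1.1 has discontinuation considered when the patient meets "one of the following conditions after consultation with the Sponsor-designated medical monitor", so the medical monitor is involved in every AST scenario in the table.
- Appendix 4 tests are open to any treatment-emergent hepatic abnormality, whichever enzyme rises, and section 9.5 allows unscheduled PK samples for hepatic laboratory abnormalities.
- The criterion of more than 2 weeks above 5X implies repeat measurement.
- Section 9.4.9 is itself discretionary after the trigger: no particular test is compulsory even at ALT ≥3X.
- AST can come from muscle. Muscle effects are a separate topic of special interest and creatine kinase is on the routine panel, so an ALT-led trigger is a defensible preference.

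Most of this stands, and it is why the point is minor. It does not supply what is missing. The Appendix 2 repeat depends on the investigator suspecting clinical significance, Appendix 4 tests are optional, and the 8.1.1 consultation comes at the discontinuation stage. None sets an AST level for starting the work-up or calls for the hepatic eCRF. The muscle argument supports a flexible work-up, which 9.4.9 already allows, more than it supports having no trigger.

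**Conclusion.** The point holds as a minor inconsistency between two linked safety sections. Through ALT or ALP, a patient meeting an 8.1.1 criterion has always met a 9.4.9 trigger; through AST, none of the four criteria ensures it. The finding concerns the wording as designed, since the SAP records that the study was stopped for futility in June 2018. It rests on the text of both sections and on the reading of the prothrombin limb stated above. The documents give no rate of isolated AST elevation, so the number of patients is unknown; it is probably small.

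A reader might infer more than the documents support:

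- **That isolated AST rises would go unmonitored.** They would not. AST is measured routinely and the general safeguards apply.
- **That potential Hy's Law cases would be missed.** They would not. The SAP definition requires TBL ≥2X ULN, which is itself a 9.4.9 trigger.
- **That AST-only cases would be absent from the hepatic CRF listing in SAP 6.13.4.** This would follow only if the CRF completion criteria copy 9.4.9, and those instructions are not in the documents.
- **That the spacing of laboratory visits makes AST follow-up worse than ALT follow-up.** The schedule is the same for both enzymes, and 9.4.9 states no retest interval for either.

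**What to change.** In Protocol 9.4.9, change the transaminase trigger from ALT ≥3X ULN to ALT or AST ≥3X ULN. Keep the sentence that ties the details of monitoring to severity and persistence, so that a rise explained by creatine kinase can be closed early.

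This is one wording change and adds no new test, because the Appendix 4 panel and the hepatic eCRF already exist. The cost is a few additional hepatic work-ups and eCRFs, their number unknown, some of which will turn out to be AST of muscle origin.
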